5.2 EXCLUSION CRITERIA

An individual who meets the following criteria will be excluded from participation in this study:

- 1. Any child with a history of endocrine disorder, heart disease, lung disease, kidney disease, digestive disease or skeletal dysplasia.
- 2. Any pre-existing chronic conditions that would prevent participants from adhering to the protocol, including oncological and psychiatric disorders.
- 3. Is undergoing or planning to undergo significant medical procedures in the next six months.
- 4. A history of severe allergic reactions, including but not limited to any of the product's ingredients.
- 5. Any child with a dairy allergy or lactose intolerance.
- 6. Has undergone any surgeries or invasive treatments in the last six months.
- 7. Has had any major illness in the last three months.
- 8. Having any planned invasive medical procedures during the study period
- 9. Currently participating in any other clinical study.
- 10. Unwilling to follow the study protocol.
- 11. Any child diagnosed with attention-deficit disorder (ADD) or attention-deficit hyperactivity disorder (ADHD).
- 12. Any child currently taking, or have they taken in the last 3 months, any prescription medication targeting ADD or ADHD (such as Adderall, Concerta, Focalin, Evekeo, or Ritalin).
- 13. Any child that is a 'fussy' eater or who the parent suspects may not tolerate consuming the test product daily for six months.

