3 OBJECTIVES AND ENDPOINTS

OBJECTIVES	ENDPOINTS	TIMEPOINTS	ASSESSED BY	JUSTIFICATION FOR ENDPOINTS
Primary				
To examine the effect of the NuBest Tall Growth Protein Powder cognitive function.	Improvement in score on assessments: • Double Trouble • Feature Match • Grammatical Reasoning • Digit Span • Token Search	Baseline and Month 6	Cognitive Battery Testing	The combination of these cognitive assessments will provide objective data on the efficacy of the product in improving specific domains of cognitive function.
Secondary				
	Increase in height			

	Maintenance of a healthy weight	Baseline, Month 2, Month 4, Month 6 (height & weight measurements)	Height measured using an Ultrasonic Height	
To investigate the impact of the NuBest Tall Growth Protein Powder on a range of health parameters, including height, weight, energy levels, immune function, and digestion.	Increase energy levels		Measuring Stadiometer	The combination of objective measurements and questionnaires will provide both independent and participant perception data on secondary health parameters.
	Improved signs of digestive health		Weight measured using a FitBit Smart Scale.	
	Increased immune	Baseline, Month 1, Month 2, Month 3, Month 4, Month 5, Month 6.		
	function (assessed via the number of times the child has been ill in the past 6 months)		Study-specific questionnaires	

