6.4 PARTICIPANT DISCONTINUATION/WITHDRAWAL FROM THE STUDY

Participants are free to withdraw from participation in the study at any time upon request.

An investigator may discontinue or withdraw a participant from the study for the following reasons:

- Pregnancy
- Significant study intervention non-compliance
- If any clinical adverse event (AE), laboratory abnormality, or other medical condition or situation occurs such that continued participation in the study would not be in the best interest of the participant
- Disease progression which requires discontinuation of the study intervention
- If the participant meets an exclusion criterion (either newly developed or not previously recognized) that precludes further study participation
- Participant should be withdrawn from the study if they start on a new drug or receive antibiotics

The reason for participant discontinuation or withdrawal from the study will be recorded on a Case Report Form (CRF). Participants who sign the informed consent form but do not receive the study intervention may be replaced. Participants who sign the informed consent form, receive the study intervention, and subsequently withdraw, or are withdrawn or discontinued from the study, will not be replaced.

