7 STATISTICAL CONSIDERATIONS

Following data collection and the completion of the trial, the data will be analyzed by Citruslabs to determine the effect of the intervention versus the placebo. Between-arm and participant repeated measures between time point statistical tests will be used to examine differences in health outcomes during the study and compared to the placebo. Percentages of people who experienced improvements will also be examined. The analysis will adopt an intent-to-treat (ITT) approach, reflecting the primary objective of assessing the effectiveness of the test product as it would be used in the general population, inclusive of all randomized participants, irrespective of adherence or protocol deviations.

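### Baseline and Month 6 illness counts are not like for like, so within-arm change and percentage improved in immune function carry a selection bias of unknown size and direction

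*Combined protocol and SAP*

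**What the plan says.** Section 3 defines the immune endpoint as increased immune "function (assessed via the number of times the child has been ill in the past 6 months"). The table is broken in the available text, but the questionnaire endpoints appear to be collected at "Baseline, Month 1, Month 2, Month 3, Month 4, Month 5, Month 6". The 6-month window thus lies wholly before entry at Baseline and wholly on study at Month 6.

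Section 5.2, exclusion 7, removes a child who "Has had any major illness in the last three months". The word *major* is not defined.

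Section 6.4 lists reasons why an investigator may withdraw a child. One is "If the participant meets an exclusion criterion (either newly developed or not previously recognized) that precludes further study participation". Another is worded more firmly: "Participant should be withdrawn from the study if they start on a new drug or receive antibiotics".

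Section 4.4 counts a child as a completer only if the Month 6 questionnaire is done. Section 7 says "Between-arm and participant repeated measures between time point statistical tests will be used to examine differences in health outcomes", and adds "Percentages of people who experienced improvements will also be examined". It adopts intention to treat, but gives no rule for a child with no Month 6 count and does not say what counts as an improvement.

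**The concern.** A within-child comparison of two counts needs both counts to cover the same kinds of event. Here they do not. Selection at entry clears major illness from half of the Baseline window. The Month 6 window is free of that restriction, but may be thinned in a different way if children who fall ill leave the study before it is measured. Both mechanisms work with no product effect and with constant illness rates through the year, so this is separate from season.

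At stake is how two planned outputs for immune function are read: the test between time points within an arm, and the percentage improved. Either could be reported as an effect of the product, or as the lack of one, when part of it reflects who was allowed in and who stayed.

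**Working it through.** The documents give no illness rate and no expected change in illness count, so there is no figure of the plan's own to reproduce. The check uses a simple model with constant rates.

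**Inputs from the documents**
- Look-back window: 6 months (Section 3).
- Part of the Baseline window cleared of major illness: 3 months (Section 5.2), so 3/6 = 50%.
- Arm size: 30 (Section 5.4).

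**Assumed inputs**
- L = 2 illnesses per child per 6 months. L cancels from the percentage change.
- s = share of illnesses that are major, 2% to 20%.
- w = chance that a major illness on study leads to withdrawal.
- a = chance that a minor illness on study leads to withdrawal, for example through antibiotics.

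**Formulas (independent Poisson counts)**
- Expected Baseline count = L(1 − s) + L·s·(3/6)
- Expected Month 6 count in completers = L(1 − s)(1 − a) + L·s·(1 − w)

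**Step 1: exclusion 7 alone (w = 0, a = 0).** The relative rise is (s/2)/(1 − s/2).

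| s | Baseline | Month 6 | Change |
|---|---|---|---|
| 2% | 1.98 | 2.00 | +1.0% |
| 5% | 1.95 | 2.00 | +2.6% |
| 10% | 1.90 | 2.00 | +5.3% |
| 20% | 1.80 | 2.00 | +11.1% |

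**Step 2: add the Section 6.4 withdrawals.** With a = 0, the change among completers is (L·s/2)(1 − 2w). It is zero at w = 0.5 and negative above that.
- s = 10%, w = 1, a = 0: 1.90 to 1.80, or −5.3%.
- s = 5%, w = 0, a = 5%: Baseline 1.95; Month 6 = 2 × 0.95 × 0.95 + 2 × 0.05 = 1.905; change −2.3%.
- s = 20%, w = 1, a = 10%: Baseline 1.80; Month 6 = 2 × 0.80 × 0.90 = 1.44; change −20.0%.

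**Step 3: size against noise.** In a simulation of 1,000,000 children with L = 2, s = 10% and no withdrawals, 41% had a higher count at Month 6, 21% the same and 38% a lower one. Without the selection, the higher and lower shares would be equal. The mean change was +0.10 with an SD of 1.98, so the standard error for an arm of 30 is 1.98/√30 = 0.36. The arm mean would rise about 61% of the time.

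**Step 4: between arms.** Exclusion 7 is applied before allocation and equally to both arms, so it is not a source of difference between them.

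**The case against.** The strongest case for leaving the plan alone has four parts.

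1. The trial's stated purpose is intervention against placebo, and that comparison is not biased by exclusion 7.
2. The shift is small against sampling noise: +0.10 against a standard error of 0.36 in the example above.
3. Major illness should be uncommon in children who must be generally healthy (Section 5.1). A rise as large as 23% needs a major share of 37.5% (0.1875/0.8125).
4. Section 7 is generic and does not name the Baseline and Month 6 illness counts as the pair to be tested.

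All four stand as limits on importance. None makes the windows match. Section 7 applies its tests between time points and its percentages to health outcomes in general, with no exception for this one. Nor does intention to treat repair the Month 6 count, because the plan describes neither follow-up after withdrawal nor a rule for missing data.

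A reader might go further and infer that illness counts must rise from Baseline to Month 6 in both arms, so that the product is made to look worse. The documents do not support this. It treats the Month 6 window as complete, whereas Section 6.4 allows or calls for withdrawal of some children who fall ill. Even with no withdrawals, the result is a shift in expectation and not a certain rise. The opposite inference, that withdrawals must produce a fall, is no better founded: one rule is discretionary, and the frequency of either is unknown.

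**Conclusion.** The point holds, and it is minor. The two illness counts cover different things: exclusion 7 clears major illness from 3 of the 6 Baseline months, and Section 6.4 may thin illness of any severity from the on-study months among completers. Within-arm change and percentage improved in immune function therefore cannot be read as product effects.

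The documents do not fix the direction or size of the bias. With no withdrawals and an assumed major share of 2% to 20%, the expected count rises by about 1% to 11%. If only major illnesses lead to withdrawal, the change is zero when half of them do and negative beyond that. Some withdrawal for minor illness can also turn it negative. These figures rest on constant rates and on shares that the plan does not give, and *major* itself is undefined.

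Exclusion 7 does not bias the randomized comparison. Withdrawals come after randomization, so the handling of withdrawn children still needs to be stated for that comparison too; nothing in the documents shows that they would differ by arm.

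**What to change.** State in Section 7 that:

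- the immune-function conclusion rests on the between-arm comparison of the on-study illness count at Month 6, using a count model with the Baseline count as a covariate;
- all illnesses reported up to withdrawal are included, among them any illness that led to withdrawal, with observed time as an offset;
- within-arm change and percentage improved are reported by arm as descriptive only, and not as evidence of a product effect.

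The second item needs on-study illnesses to be separable from earlier ones. A 6-month look-back answered at Month 3, for example, still covers 3 months before entry. The monthly questionnaire should therefore ask about illness since the previous one. The questionnaire text is not in the documents, so it may already do so.

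Restricting the within-child comparison to non-major illness is not a good substitute. *Major* has no definition to apply, and children withdrawn for antibiotics or a new drug would still be missing from one window only.

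The cost is a few sentences and, if needed, one questionnaire item. The withdrawal rules themselves are not touched. The small downside is that no within-arm immune claim can be made.

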5.3 PARTICIPANT COMPENSATION

All participants will be compensated \$150 for their time and effort in the form of a Visa gift card. Participants will also be permitted to keep the FitBit Smart Scale and the Ultrasonic Height Measuring Stadiometer.

5.4 JUSTIFICATION OF SAMPLE SIZE

60 participants, 30 each in the intervention and placebo arms, is sufficient to establish differences between the two study conditions. This will allow for meaningful between-group comparisons to adequately assess the efficacy of the test product versus placebo control.

[figure not shown]

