4 STUDY DESIGN

4.1 OVERALL DESIGN

This study is a randomized, double-blinded, placebo-controlled trial of 60 parent and child combinations i.e. 60 parents and 60 children.

Participants will be randomized into one of two arms. This study will be double-blinded; the study participants and study coordinators will be blinded to the intervention or product allocation. Arm 1 will take NuBest Tall Growth Protein Powder throughout the trial. Arm 2 will take a placebo product for the duration of the trial. Only the children will take the test product.

The parents will answer questionnaires at Baseline and on Month 1, Month 2, Month 3, Month 4, Month 5, and Month 6. Parents will provide height and weight measurements of the child at Baseline, Month 2, Month 4, and Month 6. The children will complete cognitive assessments at Baseline and Month 6. The trial will be a virtual study consisting of only virtual assessments, and the participants will follow the use instructions provided by the research team.

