6.3 RANDOMIZATION AND BLINDING

Participants will be randomized into the intervention group (NuBest Tall Growth Protein Powder) or into a placebo product control group. Randomization occurs via a randomization tool that will equally place participants into a group that will use product A or B. The research coordinator who will conduct the randomization will not know which product is the test product and which is the control.

This study will be double-blinded; the study participants and study coordinators will be blinded to the intervention or product allocation. Only the sponsor will know which product, A or B, contains the active ingredients. After the study is complete, the allocation will be unblinded prior to the analysis. Both groups will receive products that look identical.

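### No model is named for the cognitive comparison: make it an ANCOVA on the baseline score, and replace the bare claim of sufficiency in Section 5.4 with a detectable difference

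*Combined protocol and SAP*

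**What the plan says.** Section 5.4 states that "60 participants, 30 each in the intervention and placebo arms, is sufficient to establish differences between the two study conditions" and adds: "This will allow for meaningful between-group comparisons to adequately assess the efficacy of the test product versus placebo control". The visible text gives no target difference, SD, significance level, power or allowance for withdrawals. A figure that follows Section 5.4 is not reproduced in the copy reviewed, so nothing is inferred from its absence.

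Section 7 is the whole of the statistical plan. It says that "Between-arm and participant repeated measures between time point statistical tests will be used to examine differences in health outcomes during the study". It names no model, no covariate and no multiplicity rule.

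The primary endpoint in Section 3 is "Improvement in score on assessments", followed by five cognitive tests with no lead test and no composite. The synopsis says that scores will be compared across measurement points. On timing, Section 4.1 says: "The children will complete cognitive assessments at Baseline and Month 6". Section 6.1 places the baseline assessment before allocation. Section 6.3 gives equal allocation to the two products. Section 6.4 says that children who receive product "and subsequently withdraw, or are withdrawn or discontinued from the study, will not be replaced".

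**The concern.** Two things are left open that bear on each other.

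First, the analysis. The baseline cognitive score is measured before allocation, so it is a legitimate covariate, and it is probably the best single predictor of the Month 6 score. The plan brings baseline in only through general wording about improvement and repeated measures. That wording would cover a change-score test, tests over time within each arm, or a comparison of Month 6 scores. These differ in precision, and only a between-arm comparison answers the primary objective. Section 6.3 also places unblinding before the analysis, which is a further reason to fix the model in advance.

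Second, the claim. Whether 30 per arm is enough depends on the size of effect sought and on the model, and the text of Section 5.4 gives neither. A reader of a non-significant result would not know which effects the trial could reasonably have found.

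**Working it through.** **Inputs from the documents:** 30 per arm (Section 5.4), equal allocation (Section 6.3), each cognitive score measured at Baseline and Month 6 (Section 4.1), five primary tests (Section 3), no replacement after product is received (Section 6.4).

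**Assumed, because the text does not give them:** two-sided 5%, 80% power, one test, complete data, equal SD at both time points, baseline-to-Month 6 correlation r of 0.5 to 0.8. For sensitivity: 25 per arm after withdrawals, and alpha 0.05/5 = 0.01 (Bonferroni over five tests).

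**The plan's own figure.** N = 60 cannot be reproduced, because the text supplies no inputs. It was turned round into a detectable difference.

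**Month 6 scores alone.** The detectable difference in SD units is λ × √(2/n), where λ is the noncentrality that gives 80% power. With n = 30 (58 df), λ = 2.849 and √(2/30) = 0.258, so the difference is 0.736. The normal approximation, (1.960 + 0.842) × 0.258 = 0.72, agrees. Power is 48% at 0.5 SD and 21% at 0.3 SD.

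**Effect of the model.** The 0.736 is multiplied by:
- √(2(1 − r)) for a change-score test. With two time points this is the same as the arm-by-time test in a repeated-measures analysis.
- √(1 − r²) for ANCOVA, with one degree of freedom lost.

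| r | Month 6 alone | Change score | ANCOVA | ANCOVA ÷ change, √((1 + r)/2) |
|---|---|---|---|---|
| 0.5 | 0.74 | 0.736 × 1.000 = 0.74 | 0.736 × 0.866 = 0.64 | 0.87 |
| 0.7 | 0.74 | 0.736 × 0.775 = 0.57 | 0.736 × 0.714 = 0.53 | 0.92 |
| 0.8 | 0.74 | 0.736 × 0.632 = 0.47 | 0.736 × 0.600 = 0.44 | 0.95 |

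At r = 0.3 the contrast is larger: 0.87 SD for change scores against 0.70 SD for ANCOVA. At r = 0, ANCOVA gives 0.74 SD, the same as Month 6 scores alone to two decimals, so the lost degree of freedom is immaterial.

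Power at a true 0.5 SD, for r = 0.5, 0.7 and 0.8, is 59%, 76% and 89% with ANCOVA, against 48%, 69% and 85% with change scores. At 0.3 SD, ANCOVA gives 26%, 36% and 48%.

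**Withdrawals and multiplicity, Month 6 scores alone:** 0.81 SD at 25 per arm; 0.91 SD at 30 per arm and alpha 0.01; 1.00 SD with both. Multiplying by the ANCOVA factors 0.866, 0.714 and 0.600 (from unrounded values) gives 0.70, 0.58 and 0.49 SD at 25 per arm; 0.79, 0.65 and 0.55 SD at alpha 0.01; and 0.87, 0.72 and 0.60 SD with both.

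**What a confidence interval would show.** For Month 6 scores alone at 30 per arm, the 95% half-width is 2.002 × 0.258 = 0.52 SD.

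**The case against.** The strongest reply is that the plan does not commit to ignoring baseline. A reader might infer an unadjusted comparison of Month 6 scores, and so a fall from 0.74 to as little as 0.44 SD from adjusting. The documents do not support that. The endpoint is worded as improvement, the synopsis compares scores across time points, and Section 7 mentions repeated measures. Change from baseline is the natural reading, and against it the gain is only 8% at r = 0.7 and 5% at r = 0.8. This stands, and it sets the size of the point.

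A reader might also infer that the trial is shown to be underpowered. It is not. Section 5.4 names no target effect or power that the design misses, and 0.3 and 0.5 SD are benchmarks brought to the plan from outside. Nor is it right that the trial could detect only large effects: 0.74 SD is moderate to large, and a one-sided 5% test would bring it to 0.65 SD.

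Lastly, a reader might infer that effects below the detectable difference could never be ruled out. That confuses power with estimation. With a half-width of about 0.52 SD, an estimate near zero would exclude 0.6 or 0.7 SD.

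What remains is that the model is unspecified, that ANCOVA is never materially worse than either alternative, and that the visible text gives no basis for the word sufficient. The figure not reproduced after Section 5.4 might hold some basis for it. The detectable differences do not depend on that figure.

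**Conclusion.** The point holds as a should-fix on the choice of analysis, with a companion edit to the sample-size text. Prespecifying ANCOVA brings the detectable difference to 0.64–0.44 SD for r between 0.5 and 0.8, against 0.74–0.47 SD for change scores. The gain is largest if the correlation is low, and small if it is 0.7 or above.

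Baseline adjustment does not make 60 children enough for every effect of interest. Under ANCOVA, 80% power needs a correlation of about 0.73 at 0.5 SD and about 0.91 at 0.3 SD. The unqualified assurance in Section 5.4 should therefore go whichever model is used.

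All of these figures rest on the assumed significance level, power, correlations, complete data and a single test. They worsen with withdrawals or multiplicity control.

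**What to change.** **Section 7.** State that the primary between-arm analysis of each cognitive score is an ANCOVA of the Month 6 score on arm and baseline score, reported as the adjusted difference with its 95% confidence interval.

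**Section 5.4.** Replace the claim of sufficiency with wording such as: *With 30 children per arm, a two-sided 5% level, 80% power, one test and complete data, the baseline-adjusted analysis can detect a difference of about 0.64 to 0.44 SD if the correlation between baseline and Month 6 scores lies between 0.5 and 0.8. This figure rises with withdrawals and with control for five tests; for Month 6 scores alone it would be 0.74 SD, or 0.81 SD at 25 per arm, 0.91 SD at a 1% level and 1.00 SD with both. Power is limited for effects below the detectable range; for Month 6 scores alone it would be 48% at 0.5 SD and 21% at 0.3 SD. A non-significant result will be interpreted from its confidence interval.*

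The sponsor should substitute its own significance level, power and correlation where it has them, and keep anything relevant from the figure after Section 5.4. This edit neither sets a multiplicity rule nor deals with missing Month 6 scores; both still need their own text.

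**Cost.** One model, one paragraph and one degree of freedom. Enrolment, visits and assessments do not change. The stated claim becomes less favourable.
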